Research Protocol

Project Title: InterStim Implantation Rate Following Percutaneous Nerve Evaluation With Fluoroscopy versus Without.

Principal Investigator: [name] MD

Co-Investigators: [name] MD, [name] MD, [name] MD and [name] MD

Regulatory Coordinator: [name] RN, CCRC
University of Louisville, Dept of OB/GYN
Senior Research Nurse Coordinator/Research Manager for OB/GYN

Study Sites:

University of Louisville

University of Louisville HealthCare Outpatient Center (HCOC)

University of Louisville Hospital (ULH) Outpatient Surgery Center at HCOC

Jewish East Medical Center

Revised Protocol Dated March 28, 2016

Protocol Summary/Purpose:

Sacral nerve stimulation (SNS) is a well-established treatment for refractory urinary urgency, frequency, retention and urge incontinence as well as fecal incontinence. Patients whose symptoms are refractory to more conservative therapies such as behavioral modification and/or medications are candidates for SNS. The InterStim system consists of a permanent tined lead and implantable pulse generator (IPG) or battery that delivers the sacral neuromodulation. This device is typically implanted after patients have a successful response to a trial of sacral neuromodulation with a temporary lead and external battery. The temporary lead placement is known as a Percutaneous Nerve Evaluation (PNE) and is typically done in as an outpatient procedure using local anesthetic. It is standard practice to use fluoroscopy intraoperatively to confirm correct placement of the permanent lead. Additionally, some physicians also use fluoroscopy to confirm correct placement of temporary lead during PNE while others place the lead based on anatomical landmarks and expected elicited responses for S3 stimulation.

We propose a randomized control trial comparing the rate of implantation of the InterStim device following (PNE) performed with or without fluoroscopic guidance.

Objective:

To compare rates of implantation of InterStim after percutaneous nerve evaluation (PNE) with and without fluoroscopic guidance.

Hypothesis:

There will not be a significant difference in the conversion rate in patients who receive PNE placed with fluoroscopy versus those who have PNE placed without fluoroscopy.

Introduction and Background:

Sacral nerve stimulation (SNS) is a well-established treatment for refractory urinary urgency, frequency, retention and urge incontinence as well as fecal incontinence. Patients whose symptoms are refractory to more conservative therapies such as behavioral modification and/or medications are candidates for SNS. Prior to placement of the implant, patients must first undergo percutaneous nerve evaluation (PNE) and test stimulation. During this outpatient procedure the patient is placed in the prone position and a needle is inserted into the S3 foramen bilaterally under local anesthetic. Correct placement of the needle is confirmed by eliciting the appropriate nerve stimulation responses, and in some cases by the use of fluoroscopy. When correct position is achieved, a temporary monopolar percutaneous lead is placed through each needle bilaterally and the needles removed. The leads are attached to an external stimulator that is worn for a period of 3 to 7 days. Patients keep voiding diaries during the test stimulation, and if they demonstrate a 50% or greater improvement in symptoms they are eligible for implantation of the permanent timed lead and pacemaker-like stimulator, or IPG. Most studies report a 40% to 50% implantation rate following PNE (1). While some practitioners reserve fluoroscopic guidance solely for placement of the permanent timed lead, some prefer to use fluoroscopy when placing the temporary lead during PNE as well.

Methods and Procedures:

Patients with refractory urinary or fecal urgency, frequency, or incontinence undergoing peripheral nerve evaluation prior to InterStim implantation will be recruited from the HCOC Urogynecology outpatient office and will be consented for participation in the study during their preoperative office visit or on the day of their procedure. We plan to enroll approximately 200 patients in the study. Subject participation will last approximately 3 months.

Patients will be randomized just before PNE by block randomization to either Group 1 or Group 2. .

Group 1: Fluoroscopy guided PNE

Group 2: PNE without fluoroscopic guidance

Patients randomized to Group 1 will have their PNE performed in the HCOC outpatient surgery center or at the Jewish East Medical Center under local anesthetic with fluoroscopic guidance. Fluoroscopy will be used to confirm correct needle and subsequent lead placement.

Patients randomized to Group 2 will also have the PNE performed in the HCOC outpatient surgery center or at the Jewish East Medical Center under local anesthetic but no fluoroscopy will be used. (This is our current practice for PNEs.)

As is standard practice following PNE, patients will complete a 3-7 day voiding diary pre and post procedure, and if a 50% or greater improvement in symptoms (number of voids, number of incontinent episodes, or less urgency) is documented they will be eligible for implantation of the tined lead and implantable pulse generator (IPG). We will then calculate implantation rates between the two groups.

Inclusion Criteria:

- Women age ≥ 18
- English speakers
- Patients with urinary urgency, frequency, or urge incontinence refractory to at least 1 other intervention who elect to undergo PNE

Exclusion Criteria:

- Patients in whom bilateral leads cannot be placed
- Pregnant women
- Prisoners
- Less than 18 years of age

Data Sources:

- Electronic medical record at HCOC will be used to collect data

Data Collection:

The following information will be collected from the electronic medical record and entered into an encrypted excel spreadsheet:

- Age
- Race
- BMI
- Preoperative diagnosis
- Previous treatments for urinary urgency, frequency, retention, and/or urinary or fecal incontinence
- Percent improvement in symptoms as determined by pre and post PNE voiding diaries
- Whether or not InterStim implanted within 3 months of PNE
- Date of PNE
- Date of implantation of InterStim (if applicable)
- PFDI-20, PISQ-12, PFIQ-7 quality of life surveys

Data Analysis and Statistical Methods:

The primary outcome will be the difference in the rate of implantation of InterStim after PNE in each group. Secondary outcomes will identify demographic and perioperative factors associated with increased rates of implantation. Demographic factors will include age, race, previous treatments, and percent improvement in symptoms as determined by pre and post PNE voiding diaries. Continuous variables will be compared using the non-paired T-test and categorical variables will be compared using the chi-squared test.

Data Handling/Storage

All identifying information and data collected during the course of this study will be kept secure and strictly confidential. All data will be stored electronically on a password protected, encrypted laptop in the possession of the study investigators. Data will NOT be stored on a 'cloud' type server per HIPAA regulations. If data is transported, it will be transported on an encrypted device such as an encrypted thumb drive, CD, or DVD. Paper data collections forms will be utilized and data will be entered from the paper data form to an encrypted, password protected laptop or computer database. These data forms will be housed in a locked file cabinet in the fellow's office in OBGYN office in the Ambulatory Care Building with restricted access.

Potential Benefits:

We do not anticipate any direct benefits to our study participants.

Potential Risks:

Risks to PNE include bleeding, bruising, infection, and/or discomfort at the site of lead insertion as well as lead migration and a temporary tingling sensation like that of an electrical shock. Should the patient decide to proceed with implantation of the InterStim system the same risks apply as well as pain or discomfort at the implant site, device malfunction, or undesirable changes in urinary or bowel habits.

Additionally, this research study cannot practically be conducted without access and use of protected health information. Thus, the principle risk to patients involved in the study is a potential breach of confidentiality and misuse or exposure of this information. With this in mind, the investigators will conduct all research activities in such a way that maximizes data security and minimizes any risk of potential data breaches.

Protection of Human Subjects/Security of Data/Conduct of Study:

The investigators will take great care to protect and secure all study data collected for this study.

Risks for breaches of confidentiality will be minimized by entering data from the medical record or paper data collection forms to a password protected, encrypted computer database which will have limited access to the PI, Co-PIs and sub-investigators.

Personal identifiers (name, DOB, MR #) will be collected and retained in an encrypted excel spreadsheet (Key). However, all patient information will be completely de-identified by using a study code or number instead of identifiers for the purposes of data analysis and reporting.

Data will be de-identified as soon as is feasible without compromising the study. Data will be stored as an encrypted file on a password protected laptop computer or encrypted thumb drive. Data will NOT be stored on a 'cloud' type server per HIPAA regulations.

A de-identified, password protected, encrypted spread sheet will be provided to the statistician for statistical analysis. Statistical consultants will not be added to this study since they will only work with totally de-identified data and will never see actual images or medical records.

The protected health information gathered for this study will be destroyed as soon as is feasible and will not be reused or disclosed to any other person or entity, except as required by law.

The excel “key” spreadsheet listing Research ID #, name, DOB, and, MR# may be disclosed to staff at the HCOC so that they may upload the required research documents into the Allscripts electronic medical record. As soon as all data have been collected and there is no further need to return to a subject’s medical record, the Excel key(s) linking name, DOB and MR # to research ID numbers will be destroyed.

The research personnel involved in this study [name] MD, [name] MD, [name] MD, [name] MD, [name] and [name] RN, CCRC (regulatory only) are CITI and HIPAA trained. No additional personnel are involved at this time. If new research personnel are added to the study, an amendment will be submitted to and approved by the IRB before being allowed to participate in the study.

Adverse Event Reporting and Data Monitoring:

The research team will closely monitor data collection and assure confidentiality at every point during this study. The IRB and appropriate hospital research office will be notified immediately of any adverse events, including security breaches of the data, or UPIRTSOs, whether expected or unexpected.

References

1. Baxter, Chad, Kim, Ja-Hong: Contrasting the Percutaneous Nerve Evaluation Versus Staged Implantation in Sacral Neuromodulation. Curr Urol Rep. Sep 2010; 11(5): 310–314.

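### The hypothesis predicts no significant difference, but a chi-squared test of equality in about 200 patients cannot support that claim

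*Combined protocol and SAP*

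**What the plan says.** The Hypothesis section reads "There will not be a significant difference in the conversion rate in patients who receive PNE placed with fluoroscopy versus" PNE without it. The Objective is neutral: "To compare rates of implantation of InterStim after percutaneous nerve evaluation (PNE) with and without fluoroscopic guidance". In Data Analysis and Statistical Methods, "The primary outcome will be the difference in the rate of implantation of InterStim after PNE in each group". The Data Collection list shows that this is recorded per patient as yes or no: "Whether or not InterStim implanted within 3 months of PNE".

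Two methods are named: an unpaired t-test for continuous variables and, for the rest, "categorical variables will be compared using the chi-squared test". Only the second fits the primary outcome. On size, Methods and Procedures says "We plan to enroll approximately 200 patients in the study", with no calculation behind it. The Introduction gives the one rate available for planning: "Most studies report a 40% to 50% implantation rate following PNE". Of the arm without fluoroscopy, Methods and Procedures says "This is our current practice for PNEs".

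The plan gives no significance level, power, target difference, confidence interval, equivalence or non-inferiority margin, or rule for drawing a conclusion.

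**The concern.** A chi-squared test takes equal rates as its null hypothesis. A small p-value is evidence against equality; a large one is not evidence for it. A large p-value arises when the rates are similar, and also when they differ but the trial is too small to show it. The plan has no way to tell these apart. Under the hypothesis as worded, a smaller trial is more likely to be confirmed when a real difference exists.

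PNE without fluoroscopy is the site's current practice, so the practical question is whether adding fluoroscopy changes the implantation rate. A bare p > 0.05 could be read as showing that it does not, while a difference of 10–15 points in one direction or the other remained compatible with the data.

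**Working it through.** **Inputs from the plan.** About 200 patients; two groups; a 40–50% implantation rate; a chi-squared test.

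**Assumptions not in the plan.** 1:1 allocation with 100 per arm, everyone analysed, two-sided 5%. The plan gives no important difference or margin, so 10, 15 and 20 percentage points (pp) are shown as an illustrative range.

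**The figure of 200.** It cannot be reproduced, because no design inputs accompany it. Working backwards, it fits a difference of about 20 pp at 80% power: 93–97 per arm for a 20-point increase from 40–50%, without continuity correction.

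**1. Precision.** The 95% half-width for the difference is 1.96 × √(2p(1−p)/100):
- p = 0.40: 1.96 × 0.0693 = 13.6 pp
- p = 0.45: 1.96 × 0.0704 = 13.8 pp
- p = 0.50: 1.96 × 0.0707 = 13.9 pp

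Even identical observed rates would leave 10 pp inside the interval on both sides.

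**2. How often a real difference satisfies the hypothesis.** Exact enumeration of two binomials with 100 per arm, one arm at 40%, 45% or 50% and the other lower, gives the chance of p > 0.05:

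| True difference | Pearson chi-squared | With continuity correction |
|---|---|---|
| 10 pp | 68–69% | 74% |
| 15 pp | 37–41% | 44–47% |
| 20 pp | 12–17% | 16–21% |

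With the other arm higher, the Pearson figures are 69%, 41% and 17%.

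**3. An example.** Take 50/100 implanted with fluoroscopy and 37/100 without.
- Pooled rate 0.435; z = 0.13/√(2 × 0.435 × 0.565/100) = 0.13/0.0701 = 1.85; p = 0.064.
- Unpooled SE = √(0.50 × 0.50/100 + 0.37 × 0.63/100) = 0.0695; 95% CI = 13 ± 13.6, or −0.6 to +26.6 pp.

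This result fits the hypothesis, yet it is compatible with fluoroscopy raising implantation by more than 25 points.

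**4. If the true rates are equal, what could be excluded?** Exact enumeration with the Wald 95% interval:

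| Difference | Excluded in one given direction | Whole interval inside ± that value |
|---|---|---|
| 10 pp | 31% | 0% |
| 15 pp | 58–59% | 17% |
| 20 pp | 82–83% | 64–65% |

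**5. What a claim of no important difference would need.** For 80% power with the whole 95% interval inside ±m and equal true rates, each side may fail 10% of the time, so z = 1.282.
- Smallest margin at 100 per arm: (1.960 + 1.282) × SE = 22.5–22.9 pp.
- Total patients: 2 × (1.960 + 1.282)² × 2p(1−p)/m², with each arm rounded up: 450–468 for ±15 pp and 1,010–1,052 for ±10 pp.
- With a 90% interval (two one-sided 5% tests), 1.645 replaces 1.960: 366–382 for ±15 pp and 824–858 for ±10 pp.

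**The case against.** The case for a lesser criticism is that one sentence carries the problem. The Objective and the primary outcome are neutral, and chi-squared is a valid test for comparing two rates. Nothing says that p > 0.05 will be reported as equivalence, and the Hypothesis may be no more than the investigators' expectation. The interval can be calculated afterwards from the two arm counts. The 10–15 point range is not the plan's. At 20 points the trial does better: 82–83% chance of exclusion in one given direction, and 190–198 patients in total would give 80% power for non-inferiority at one-sided 2.5%. The 90% interval convention also lowers the cost of an equivalence claim.

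Several of these points stand. The 10–15 points are illustrative. If 20 points were the smallest difference of interest, 200 patients would be roughly adequate for a one-sided claim. A non-significant result need not leave both directions open: the example above excludes −10, and no possible result at 100 per arm gives a 95% interval containing both −15 and +15. Under the 90% convention, the chance of the whole interval lying inside the margin is still 0% at ±10 and only 38–39% at ±15.

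The main point is unaffected. This is the plan's only stated hypothesis, the named test cannot support it at any margin, and nothing limits what a non-significant result may be said to show. Leaving the interval and its interpretation until after the data are seen leaves the main conclusion open to choice.

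**Conclusion.** The concern holds. The stated hypothesis and the named test do not match, and following the plan as written lets any non-significant p-value confirm the hypothesis. That mismatch depends on no numerical assumption.

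The size of the problem rests on 100 per arm, full analysis, two-sided 5% and the cited 40–50% rate. Under these, the trial estimates the difference to within about ±14 points and cannot reliably exclude 10–15 points. The assumptions favour the trial: unequal allocation, or loss of patients in whom bilateral leads cannot be placed, would widen the interval. The number 200 is unjustified, but it has not been shown to be miscalculated. Because the trial's main conclusion is affected, the text should be corrected before data are analysed.

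**What to change.** Keep about 200 patients and change the Hypothesis and Data Analysis sections:

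1. Reword the hypothesis as a question of size, in line with the Objective: by how much does the implantation rate differ with and without fluoroscopy?
2. Make the primary analysis the risk difference, Group 1 (fluoroscopy) minus Group 2 (no fluoroscopy), with a two-sided 95% confidence interval. The chi-squared p-value may accompany it.
3. State that p > 0.05 is not evidence of no difference and that equivalence will not be claimed.
4. State the expected precision: about ±14 points at 100 per arm and a 40–50% rate.

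This takes about four sentences and needs no extra patients or data. The cost is a more modest claim and a result that may be inconclusive.

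If the sponsor prefers to keep a claim of no important difference, it should be allowed only when the whole interval lies within a two-sided margin that is clinically justified and fixed before data are examined; otherwise the result is inconclusive. That route suits 200 patients poorly. With a 95% interval, any margin below about 22 points needs more patients for 80% power. If a 90% interval is chosen instead, the plan should say so in advance; the smallest margin at 200 is then about 20.3–20.7 points, from (1.645 + 1.282) × SE.

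### Block randomisation is described without block size, stratification or concealment, and neither venue nor operator is on the data list, so next allocations may be predictable and an imbalance could not be seen or adjusted for in the planned dataset

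*Combined protocol and SAP*

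**What the plan says.** The Methods and Procedures section gives the whole allocation method in one sentence: "Patients will be randomized just before PNE by block randomization to either Group 1 or Group 2". It states no block size, stratification factor, number of lists, allocation ratio or means of concealment. The same section says that patients "will be consented for participation in the study during their preoperative office visit or on the day of their procedure", and gives the size: "We plan to enroll approximately 200 patients in the study".

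Both arms share two venues. For fluoroscopy, "Patients randomized to Group 1 will have their PNE performed in the HCOC outpatient surgery center or at the Jewish East Medical Center"; for the comparator, "Patients randomized to Group 2 will also have the PNE performed in the HCOC outpatient surgery center or at the Jewish East Medical Center". PNE without fluoroscopy is the local habit ("This is our current practice for PNEs"). The Protocol Summary/Purpose says that, where fluoroscopy is not used for PNE, physicians "others place the lead based on anatomical landmarks and expected elicited responses for S3 stimulation".

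The Data Collection section begins "The following information will be collected from the electronic medical record and entered into an encrypted excel spreadsheet". It then lists age, race, BMI, diagnosis, previous treatments, percent improvement, implantation within 3 months, dates of PNE and implantation, and three questionnaires. Venue and operator are not among them. Data Analysis and Statistical Methods plans t-tests and chi-squared tests without adjustment. It also promises a secondary look at perioperative factors, but names none. The section on protection of subjects and data gives the statistician a de-identified spreadsheet and has the identity key destroyed once the medical record is no longer needed.

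**The concern.** There are two separate issues.

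**Predictable allocation.** Whoever performs PNE knows whether fluoroscopy is used, so past assignments are visible to the procedure team. In blocks of fixed size, the last assignments follow from the earlier ones. Where consent is taken on the procedure day, someone who knows the next arm could choose whom to approach. That is a route to systematic difference between the arms, and no analysis can reliably repair it. The protocol states no safeguard.

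**Unrecorded venue and operator.** Blocking alone balances arm totals, not the mix of venues or operators within arms. If either factor affects implantation, an imbalance would be invisible in the planned spreadsheet and the analyst could not adjust for it. The same gap leaves the secondary aim on perioperative factors with nothing clearly perioperative to analyse beyond procedure dates.

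**Working it through.** **Inputs.** From the protocol: about 200 patients, two venues open to both arms, a background implantation rate of 40% to 50% (midpoint 45% used). Assumed, because the protocol is silent: 1:1 allocation (100 per arm), two-sided 5% level, venue share, venue effect on implantation, and block size. The enrolment figure comes with no alpha, power or target difference, so there is no stated calculation to reproduce. For orientation, 100 per arm gives about 81% to 83% power for a 20-point difference from a 40% to 50% base rate.

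**1. Predictability.** In a balanced block of 2m, an assignment is certain once one arm is used up. The expected number of certain assignments is 2m/(m+1).
- Block of 2 (m=1): 1 of 2 = 50%
- Block of 4 (m=2): 1.333 of 4 = 33%. Check: AABB, ABAB and ABBA leave 2, 1 and 1 certain, mean 4/3; the mirror images give the same.
- Block of 6 (m=3): 1.5 of 6 = 25%

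Over 200 patients that is about 100, 67 or 50 assignments. This holds only if the size is fixed and known or inferred, and every past assignment is seen.

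**2. Chance imbalance in venue.** For venue share s, the SD of the between-arm difference in share is √[s(1−s)(1/100+1/100)(200/199)].
- s = 0.5: SD 7.1 points, 95% range ±13.9 points, and a 16% chance of 10 points or more
- s = 0.2: SD 5.7 points, ±11.1 points, 8% chance

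**3. Shift in the arm difference** (imbalance × assumed venue effect, s = 0.5):
- 10-point effect: 0.139 × 0.10 = ±1.4 points
- 20-point effect: 0.139 × 0.20 = ±2.8 points
- 30-point effect: 0.139 × 0.30 = ±4.2 points

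These are 95% ranges, not maxima, and they do not come on top of the standard error. The sampling SE is √(2×0.45×0.55/100) = 7.0 points and already contains them. At a 20-point effect the venue part has SD 0.0709 × 0.20 = 1.4 points, or (1.42/7.04)² = 4% of the variance. Removing it would cut the SE by 1 − √(1−0.041) = 2%.

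**4. Simulated power** for a true 20-point arm difference (6,000 trials per scenario, blocks of 4, venue split 50/50, adjustment by Mantel-Haenszel):

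| Venue effect | Unstratified, unadjusted | Unstratified, adjusted | Stratified, adjusted |
|---|---|---|---|
| 20 points | 82.1% | 82.7% | 83.0% |
| 40 points | 82.6% | 88.1% | 89.0% |

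The Monte Carlo SE of each figure is about √(0.82×0.18/6000) = 0.5 point, so the 0.9-point gain in the first row is barely distinguishable from none; the 6.4-point gain in the second row is real. With no true difference, the unstratified, unadjusted test rejected in 5.4% to 5.8% of trials, with mean error −0.04 and +0.14 points: no bias. Stratifying but leaving the test unadjusted gave 3.7% rejection at a 40-point effect, which is conservative, so the analysis should follow the stratification.

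**The case against.** The strongest reply is that most of this is missing detail, not a flawed design, and that venue imbalance hardly matters. Much of that stands, and several stronger readings should be resisted.

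- **A single unstratified list.** A reader might infer one from the text. The protocol only fails to describe stratification; separate lists per venue are not ruled out.
- **Imbalance beyond correction.** A reader might infer this from the data list. But the date of PNE is collected, and the key links each patient to the record until it is destroyed, so venue and operator may be retrievable until then. Whether the HCOC record holds them for procedures at Jewish East is not stated.
- **An operator-dependent procedure with several operators.** This is a fair inference from placement by landmarks and responses and from the five MD investigators listed. The protocol never says who or how many perform PNE. It also describes elicited responses as the general way to confirm needle position, not as peculiar to the arm without fluoroscopy. Venue lists would not balance operators in any case.
- **Bias from chance imbalance.** Randomisation excludes this, and steps 3 and 4 of the working show how small the loss is at a moderate venue effect. Nothing in the protocol shows that venue affects implantation at all.
- **Selective enrolment as a fact.** The protocol does not say that blocks are fixed, that their size is known or that staff track assignments. Same-day consent is one of two options. What can be said is that no safeguard is described.

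Predictability is also a different matter from venue stratification and is not cured by it. What remains is still more than a reporting gap: the missing fields limit a stated secondary aim, and the selection route can be largely closed at almost no cost.

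**Conclusion.** The concern holds in a limited form, at minor to moderate severity. The unstated block scheme and concealment carry most of the weight. With fixed blocks and visible past assignments, a quarter to a half of allocations could be known in advance for blocks of 6 down to 2. Any resulting bias cannot be sized from the protocol, in either amount or direction. The missing venue and operator fields, with unadjusted tests, mean that the planned dataset could neither reveal nor correct an imbalance. On precision alone the cost is small: about 1 power point at an assumed 20-point venue effect and about 6 at 40 points, with an assumed even split between venues and 100 per arm. Recording venue and adjusting recovers most of that gain even without stratified lists.

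**What to change.** 1. State the allocation method: permuted blocks of randomly varied size, with a separate list for each venue, and the sizes withheld from those who enrol and treat. This assumes that the venue is settled before allocation, which randomising just before PNE suggests.
2. Release each assignment only after consent and eligibility are recorded. The exclusion for failed bilateral lead placement can be judged only during the procedure, so the rule applies to the criteria that can be checked beforehand.
3. Add venue and operator to the Data Collection list, and fill both fields before the key is destroyed. Both also serve the secondary aim on perioperative factors.
4. Pre-specify a venue-stratified primary comparison, for example Mantel-Haenszel, with operator as a sensitivity adjustment.

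The cost is two lists instead of one, two data fields and possibly a few patients' imbalance in arm totals. An unfinished block leaves at most half its size: with blocks of up to 6, that is 3 per list, so 6 over two lists against 3 over one.

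### An exclusion that is fully known only during PNE, after randomisation, can remove randomised patients from the primary comparison at a step where the arms differ

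*Combined protocol and SAP*

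**What the plan says.** Methods and Procedures sets the order of events: "Patients will be randomized just before PNE by block randomization to either Group 1 or Group 2". Introduction and Background describes the placement step within the procedure: "When correct position is achieved, a temporary monopolar percutaneous lead is placed through each needle bilaterally and the needles removed".

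The arms differ at that step. For Group 1, Methods and Procedures states: "Fluoroscopy will be used to confirm correct needle and subsequent lead placement". Group 2 has the procedure "under local anesthetic but no fluoroscopy will be used".

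The first entry under Exclusion Criteria is "Patients in whom bilateral leads cannot be placed". The other three entries (pregnancy, prisoner status, age under 18) are facts about the patient at baseline.

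Data Analysis and Statistical Methods defines the endpoint: "The primary outcome will be the difference in the rate of implantation of InterStim after PNE in each group". It gives no denominator, no analysis set and no rule for a randomised patient whose placement fails or is one-sided. The listed data items include "Whether or not InterStim implanted within 3 months of PNE" but not whether bilateral placement succeeded.

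**The concern.** Whether both leads can be placed is, for at least some patients, an outcome of the randomised procedure. Excluding patients on that outcome conditions the primary comparison on an event that follows allocation and that the allocated technique may influence. The groups left to compare are then no longer the groups that randomisation made comparable.

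Two kinds of error could follow. If fluoroscopy changes the chance of successful placement, that is one way it could change the implantation rate, and dropping the failures takes that effect out of the result. This would favour the stated hypothesis of no difference. Alternatively, if one technique gets leads into patients who are unlikely to go on to implantation, those patients stay in one arm and are removed from the other, which creates a difference that does not exist. Because the plan does not say who is counted, the choice could also be made after implantation results are known.

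**Working it through.** **The text, step by step**

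1. Randomisation precedes PNE, and lead placement is a step within PNE (Methods and Procedures; Introduction and Background). Failure of bilateral placement is therefore fully known only after allocation, although some anatomical reasons might be known earlier.
2. Fluoroscopy is used at that step in one arm only. The documents do not show that failure differs by arm, but they give no ground to assume it does not.
3. The criterion has no time limit, and no as-randomised set is defined.
4. The wording of the comparison does not settle the matter. Methods and Procedures describes groups by randomisation. The Hypothesis speaks of conversion "in patients who receive PNE placed with fluoroscopy versus those who have PNE placed without fluoroscopy", which can be read as covering only patients whose leads were placed.

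**Inputs for an illustration**

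- From the documents: about 200 patients; a background implantation rate of 40% to 50%. The 200 has no stated derivation, so there is no plan figure to reproduce.
- Assumed: exclusion applied after allocation; 100 per arm (no allocation ratio is stated); implantation rate among placed patients *r* = 0.45, the midpoint of the range; rate among failures *q* = 0 unless noted; failure shares *f1* (with fluoroscopy) and *f2* (without). All values of *f* and *q* are assumptions.
- Standard error of the difference: sqrt(2 × 0.45 × 0.55 / 100) = 7.04 points.

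**A. A real difference is hidden**

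The as-randomised rate is *r*(1 − *f*) + *qf*. After exclusion both arms show *r*, so the observed difference is 0 and the hidden difference is (*r* − *q*)(*f2* − *f1*).

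| *f1* v *f2* | *q* | As-randomised rates | Hidden difference |
|---|---|---|---|
| 5% v 5% | 0 | 42.75% v 42.75% | 0 |
| 2% v 5% | 0 | 44.1% v 42.75% | 1.35 points |
| 2% v 10% | 0 | 44.1% v 40.5% | 3.6 points |
| 2% v 10% | 0.20 | 44.5% v 42.5% | 2.0 points |
| 2% v 20% (outer case) | 0 | 44.1% v 36.0% | 8.1 points |
| 2% v 20% (outer case) | 0.20 | 44.5% v 40.0% | 4.5 points |
| any | 0.45 | 45% v 45% | 0 |

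With *r* from 0.40 to 0.50 and *q* = 0, the 2% v 10% case runs from 3.2 to 4.0 points.

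**B. A false difference is created**

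Suppose the extra patients placed in only one arm never go on to implantation. Both arms then have the same as-randomised rate, *p* = 0.45(1 − max *f*), and exclusion gives *p*/(1 − *f1*) v *p*/(1 − *f2*).

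- 2% v 10%: *p* = 40.5%. After exclusion 41.3% v 45.0%, a false deficit for fluoroscopy of 3.7 points. Standard error 7.23 points at 98 v 90 patients, z = −0.51, rejection at an assumed two-sided 5% level 8.0%.
- 2% v 20%: *p* = 36.0%. After exclusion 36.7% v 45.0%, a false deficit of 8.3 points. Standard error 7.39 points at 98 v 80, z = −1.12, rejection 20.1%.
- Softer version, with those extra patients implanted at 20% in either arm: at 2% v 10%, (0.90 × 0.45 + 0.08 × 0.20)/0.98 = 43.0% v 45.0%, a 2.0-point deficit with 5.9% rejection. At 2% v 20%, (0.80 × 0.45 + 0.18 × 0.20)/0.98 = 40.4% v 45.0%, a 4.6-point deficit with about 9% rejection.

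Rejection rates use the normal approximation.

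**Direction.** Swapping the failure rates reverses every sign: 10% v 2% shifts the result by 3.6 to 3.7 points in favour of fluoroscopy, and 20% v 2% by 8.1 to 8.3.

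**The case against.** The strongest reply is that the protocol never says randomised patients will be dropped. It describes groups by assignment and calculates rates between those groups, so the plainest reading is a comparison as randomised. The Hypothesis phrase may merely name the two techniques. This is a fair reading of the group wording. It does not remove the problem, because a listed exclusion takes patients out before any rate is calculated, and the text nowhere puts them back.

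The second reply is that the numbers have no anchor: no failure rate, no implantation rate among failures, no evidence of a difference by arm. That stands. The 20% false-positive figure combines an outer failure rate with the extreme assumption that none of the extra patients is implanted; the softer version above roughly halves it. Outside the outer case, no shift exceeds about half a standard error, and zero is possible.

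The 45% anchor is also uncertain, since the background rate is given as following PNE without saying whether failed placements are counted. If 45% is instead taken as the as-randomised rate in both arms with *q* = 0, 2% v 10% gives 0.45/0.98 = 45.9% v 0.45/0.90 = 50.0%, a false 4.1 points, so the conclusion does not change.

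Finally, placement outcome may be recoverable from the medical record or from the paper forms mentioned under Data Handling/Storage, whose content is not shown. That is so, and it makes the missing data item the lesser part of this point.

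**Conclusion.** The concern holds and should be fixed before results are known. What is certain is the gap in the text: a criterion that can be fully applied only after allocation, at a step where the arms differ, with no as-randomised set to keep those patients in. Bias is possible, not shown. Equal failure rates with similar patients, or failures implanted at the same rate as placed patients, would give none.

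Under the stated assumptions, moderate cases shift the difference by about 1 to 4 points, up to about 0.5 of the 7.04-point standard error. The outer 2% v 20% case reaches 8.1 to 8.3 points (8.27 / 7.04 = about 1.2 standard errors). The mirror cases are equally large in the other direction. The case for a mandatory change rests on the undefined denominator of the only primary comparison, not on these figures.

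**What to change.** 1. Limit the criterion to reasons known before randomisation, or remove it as a ground for dropping randomised patients.
2. State in Data Analysis and Statistical Methods that the primary analysis includes every randomised patient in the assigned group. Patients without bilateral leads stay in the denominator and count as implanted only if InterStim is implanted within 3 months of PNE. That window is now only a data item, so this also writes it into the primary outcome.
3. Add bilateral placement (yes/no) to the data items and report it by arm.
4. Keep the bilaterally placed set as a sensitivity analysis. This is useful but secondary to items 1 and 2.

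**Cost.** Protocol wording, one field, and record review for patients without bilateral leads: 2 + 10 = 12 of 200 at 2% v 10%, or 2 + 20 = 22 of 200 at 2% v 20%. No visits are added, because implantation within 3 months already comes from the medical record. The downside is a lower reported rate. If 45% applies to placed patients and no failures are implanted, it falls by 0.45 × *f*: 0.9 points at 2% failure, 4.5 at 10% and 9.0 at 20%.
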